- Within 72 hours of mechanical ventilation for a diagnosis of ARDS (moderate and severe) based on the Berlin definition⁴⁷
 - Within 1 week of a known clinical insult or new or worsening respiratory symptoms
 - Bilateral opacities on CXR which are not fully explained by effusions, lobar/lung collapse or nodules
 - Respiratory failure not fully explained by cardiac failure or fluid overload
 - $\text{PaO}_2/\text{FiO}_2 < 200$ mmHg with $\text{PEEP} \geq 5$ cmH₂O

Exclusion criteria

- > 72 hours since diagnosis of ARDS
- > 10 days of continuous mechanical ventilation
- < 16 years of age
- Barotrauma (pneumothorax, pneumomediastinum, subcutaneous emphysema or any intercostal catheter for the treatment of air leak)
- Significant chest trauma i.e. multiple rib fractures
- Active bronchospasm or a history of significant chronic obstructive pulmonary disease or asthma
- Clinical suspicion for significant restrictive lung disease (history of pulmonary fibrosis or suggestive pulmonary function tests)
- Moderate or severe traumatic brain injury, the presence of an intracranial pressure monitor, or any medical condition associated with a clinical suspicion of raised intracranial pressure
- Unstable cardiovascular status defined as sustained heart rate < 40 or > 140 bpm, ventricular tachycardia, or SBP < 80 mmHg
- Pregnancy
- Receiving ECMO
- Receiving high frequency oscillatory ventilation
- Death is deemed imminent and inevitable
- The treating physician believes it is not in the best interest of the patient to be enrolled in the trial
- Consent not obtained or refused by patient's legal surrogate

Patient screening

Patients will be screened for eligibility criteria in 25-30 ICUs in Australia and New Zealand.

Informed consent

Patients will be unable to provide prospective informed consent, as they will be sedated and receiving mechanical ventilation. Informed consent will be obtained from the most appropriate Person Responsible, in accordance with section 4.4.10 of the NHMRC National Statement, and with variations according to state and territory legislations (and also as appropriate for New Zealand). Delayed consent for long-term follow up will be sought from the participant when they have suitably recovered capacity.

Enrolment and randomisation

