Titration of the FiO₂ and PEEP: The FiO₂ and PEEP should be set using the table of allowable FiO₂ and PEEP combinations as a guide. The PEEP level in this table represents the PEEP level set on the ventilator, not total PEEP. The settings should be as far to the left of this chart as possible, thereby using the lowest combination of FiO₂ and PEEP possible while maintaining oxygenation within the target range.

If the SaO₂ is < 90% (or PaO₂ < 60 mmHg, if available), the patient should be changed to the FiO₂ and PEEP combination to the right of the current settings. If the patient has a significant desaturation, it is permissible to rapidly increase the PEEP/FiO₂ from left to the right of the chart as quickly as required to achieve a satisfactory oxygen saturation, then titrate the PEEP/FiO₂ to achieve a SaO₂ 90 – 95%.

FiO ₂	0.3	0.4	0.4	0.5	0.5	0.6	0.7	0.7	0.7	0.8	0.9	0.9	0.9	1.0
PEEP (cmH ₂ O)	5	5	8	8	10	10	10	12	14	14	14	16	18	18-24

If the SaO₂ is > 95% (or PaO₂ > 80 mmHg, if available), the patient should be changed to the FiO₂ and PEEP combination to the left of the current settings. If this leads to a reduction in PEEP, it is preferable not to reduce the PEEP again **before 4 hours have passed.**

Ventilation during patient transfers: Mechanical ventilation should continue to adhere to this control group strategy during patient transfers (to diagnostic or therapeutic procedures outside the ICU) where possible. However if the patient receives mechanical ventilation using either a manual (hand-bagging) circuit or a transport ventilator that is not practically able to deliver the control group mechanical ventilation settings, patients may be ventilated using alternative means whilst away from the ICU. Resumption of control group mechanical ventilation should occur as soon as possible after the transfer.

Specific measurements on Day 3 in the control group

Patients in both groups should have 2 things measured on day 3:

1. Static respiratory compliance should be measured (see page 22 for technique).
2. Specimens of blood and BAL should be collected (see below) – **after** static respiratory compliance has been measured. The BAL should be collected using the same technique as was used at baseline.

Transition from controlled to spontaneous mechanical ventilation in the control group

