Please see the section below on “Weaning of mechanical ventilation for both groups”

Intervention group (PHARLAP) mechanical ventilation

Initial commencement of mechanical ventilation in the PHARLAP group

Mode: After randomisation, patients should be commenced in either Assist-Control (A/C) or Synchronised Intermittent Mandatory Ventilation (SIMV) using Pressure Control mode. All patients should be commenced in controlled rate ventilation, even if this requires additional sedation and/or neuromuscular blocking drugs. The PEEP level should remain at the pre-randomisation level.

The combined open lung procedure in the PHARLAP group (see Figure 1)

The initial procedure of the PHARLAP mechanical ventilation strategy should be to perform the combined open lung procedure which consists of (1) a staircase recruitment manoeuvre (SRM), followed by (2) a PEEP titration manoeuvre, and followed by (3) a brief recruitment manoeuvre (see Figure 1). This initial combined open lung procedure should be performed within 4 hours of randomisation.

This will then be followed by PHARLAP strategy mechanical ventilation.

The combined open lung procedure should be performed after assessment by an intensivist or registrar and when haemodynamic resuscitation is complete and circulatory parameters are stable. If vasopressors or inotropes are being used, a small transient increase prior to the combined open lung procedure will minimise any hypotension.

The **contraindications to a recruitment manoeuvre** (both the staircase and the brief manoeuvre) are:

- Mean systemic blood pressure < 60 mmHg despite attempts to augment BP with vasopressors/fluids.
- An active air leak through an intercostal catheter.
- Any radiographical evidence of pneumatoceles, subpleural cysts, or pericardial or mediastinal emphysema.
- Subcutaneous emphysema not related to trauma, surgical procedures, or ICU procedures.
- A supraventricular tachycardia associated with a mean systemic blood pressure < 70 mmHg, or any ventricular tachycardia.

If a patient has a contraindication to the combined open lung procedure, all other aspects of PHARLAP mechanical ventilation should be continued until the contraindication has resolved (when the combined open lung procedure should then be performed).

The combined open lung procedure should be performed as follows:

(1) Staircase recruitment manoeuvre (SRM):

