The mechanical ventilator settings should be Pressure Control with an inspiratory pressure of 15 ± 3 cmH₂O depending on tidal volume achieved (pre-SRM tidal volume target 4-6 ml/kg PBW). The PEEP level should be left at the level it had been immediately prior to this procedure. The FiO₂ should be adjusted (usually by turning it down) until the SaO₂ is stable between 90-92%. This may take several (often 15-30 minutes). The high pressure alarm should be set to 65 cmH₂O and the low tidal volume and minute ventilation alarms reduced to < 25% of the current settings.

Once the FiO₂ is stable (ie. no change for 3 minutes), the PEEP should be increased from the pre-randomisation baseline to 20 cmH₂O. In a stepwise fashion, this should be increased after 2 minutes to 30 cmH₂O (for 2 minutes) and then 40 cmH₂O (for 2 minutes), unless there is occurrence of (a) haemodynamic instability (defined as heart rate < 40 or > 140 bpm, ventricular tachycardia, or systolic blood pressure (SBP) < 80 mmHg), (b) marked oxygen desaturation (SaO₂ < 85%) or (c) new air leak through an intercostal catheter. The tidal volume should not be adjusted at each PEEP level, unless the tidal volume is > 6 ml/kg PBW.

The patient may cough or become restless at high PEEP levels. This may be due to expansion of collapsed lung and does not require the SRM to be discontinued. Transient reductions in tidal volume and minute ventilation are to be expected as the PEEP levels are increased. Sometimes the patient will require additional sedation.

If haemodynamic instability, marked oxygen desaturation or a new air leak occurs during the SRM, the SRM should be abandoned (with no further increases in PEEP occurring above the level where this occurred). If the

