- If pH remains < 7.15 (after above) and the patient is sedated as required, bicarbonate may then be considered. If the acidosis is predominantly metabolic, continuous renal replacement therapy may be required at this point.

If pH remains < 7.15 (after above) the tidal volume may be increased further but the PEEP should be reduced to maintain P_{plat} ≤ 35 cmH₂O.

Titration of the FiO₂ and PEEP: The PEEP should be left on the daily optimal PEEP determined by the most recent combined open lung procedure. The FiO₂ should be increased or decreased as required to maintain the SaO₂ aim. From day 6 onwards (i.e. after the 5 day period of performing combined open lung procedures has finished) the optimal PEEP should be set at 15 cmH₂O (or higher if clinically appropriate) unless the patient meets the readiness for weaning criteria.

Ongoing recruitment manoeuvres in the PHARLAP group

Combined open lung procedure: Subsequent combined open lung procedures (each being an SRM, a PEEP titration manoeuvre and a brief recruitment manoeuvre) should be performed daily for 5 days, unless the patient meets one of the following criteria to omit a combined open lung procedure:

- (a) readiness for weaning criteria are met (see below),
- (b) lack of improvement in static lung compliance criteria are met (on day 3, see below),
- (c) there is a contraindication to a recruitment manoeuvre (see above), or
- (d) it is the 6th day after enrolment (ie. 5 days of combined open lung procedures have occurred).

The initial combined open lung procedure should be performed within 4 hours of randomisation but subsequent combined open lung procedures should be performed during the daytime period (preferably during or soon after the morning or ICU ward round) such that one is performed on each consecutive chart day (unless the patient meets one of these criteria to omit a combined open lung procedure).

The daily combined open lung procedure should be performed as it was on the initial occasion, however each day there may be a different maximum tolerated PEEP, a different de-recruitment PEEP and a different daily optimal PEEP level determined. There should also be a different precise SaO₂ target determined 1 hour after the combined open lung procedure and which should be the new daily precise SaO₂ target. Each of these will then remain until a subsequent combined open lung procedure is performed (usually 24 hours later).

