Neither the combined open lung procedure nor independently performed SRMs should be performed at times other than this daily morning intervention.

The **lack of improvement in static lung compliance** definition will be met if the static lung compliance after the staircase recruitment manoeuvre on day 3 is lower than the static lung compliance assessed prior to the performance of the initial (day 1) combined open lung procedure. Any patient who meets this criterion will have no further combined open lung procedures or brief recruitment manoeuvres and should have the PEEP set on 15 cmH₂O (or higher if clinically appropriate) unless the patient meets the readiness for weaning criteria.

No combined open lung procedures or brief recruitment manoeuvres should be performed after day 5. If the patient has not met readiness for weaning criteria, the optimal PEEP should be set at 15 cmH₂O (or higher if clinically appropriate) unless the patient meets the readiness for weaning criteria.

Desaturation: We recommend patients receive a chest x-ray for significant persistent desaturation to rule out barotrauma before a brief recruitment manoeuvre or further combined open lung procedures are performed.

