- The PEEP should be increased to the maximum tolerated PEEP determined during the most recently performed SRM, left at that level for 2 minutes, and then immediately returned to the daily optimal PEEP determined by that same SRM.

If an oxygen desaturation ($\geq 2\%$ below the daily precise SaO₂ target) occurs with no clear precipitating event (ie. potentially a deterioration in lung function), the brief recruitment manoeuvre should be performed as follows:

- The PEEP should be increased to the maximum tolerated PEEP determined during the most recently performed SRM, left at that level for 2 minutes, and then immediately returned to 2.5 cmH₂O (rounded up by 0.5 if the ventilator does not use 0.5 cmH₂O settings) higher than the previous daily optimal PEEP set during that SRM.
- This new PEEP level should be considered the new daily optimal PEEP level for the subsequent part of that day until the next SRM is performed. The FiO₂ should then be decreased as required to maintain the SaO₂ aim.
- The PEEP should not be set higher than 25 cmH₂O at any time during the study (with the exception of the staircase recruitment manoeuvre).

Brief recruitment manoeuvres should not be repeated more frequently than 2 hourly and not more than a maximum of 4 manoeuvres per 24 hours.

Ventilation during patient transfers: Mechanical ventilation should continue to adhere to this PHARLAP group strategy during patient transfers (to diagnostic or therapeutic procedures outside the ICU) where possible. However if the patient receives mechanical ventilation using either a manual (hand-bagging) circuit or a transport ventilator that is not practically able to deliver the PHARLAP group mechanical ventilation settings, patients may be ventilated using alternative means whilst away from the ICU. Resumption of PHARLAP group mechanical ventilation (including performance of a brief recruitment manoeuvre if indicated)

should occur as soon as possible after the transfer. A brief recruitment manoeuvre will usually be required (see above on this page).

Specific measurements on Day 3 in the PHARLAP group

Patients in both groups should have 2 things measured on day 3:

1. Static respiratory compliance should be measured (see page 22 for technique).
2. Specimens of blood and BAL should be collected (see below) – **after** static respiratory compliance has been measured. The BAL should be collected using the same technique as was used at baseline.

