If haemodynamic instability occurs during the combined open lung procedure (mainly during the SRM), vasopressors should be considered initially. Intravenous fluid boluses should be administered if vasopressor requirements increase rapidly.

Use of corticosteroids in both groups

Steroids should not be used specifically for ARDS after day 7⁵¹.

Other interventions in both groups

All other interventions will not be standardised. Given the possibility of confounding by different utilisation rates of various interventions between groups, data will be collected on haemodynamics (daily central venous pressure, blood pressure and heart rate), fluid balance, pulmonary artery catheter usage, intravenous bicarbonate usage, renal replacement therapy usage, neuromuscular blocking drug usage, corticosteroid usage and hypoxaemic rescue therapy usage.

Discontinuation of treatment

Patients in both groups will receive their assigned ventilator strategy until any of the following occur:

1. The patient is no longer receiving mechanical ventilation
2. The patient dies or is discharged from the Intensive Care Unit
3. The patient or surrogate decision-maker withdraws informed consent.

Table of events

Please see Appendix 3

Laboratory sampling

Blood (10 ml centrifuged to isolate plasma) and BAL (10 ml taken using the technique described above) samples will be collected and stored -80°C at each site at baseline and day 3. Samples will be shipped in 2 batches to a central processing laboratory (Flinders Medical Centre) for quantification of IL-6, IL-8 and protein concentration by blinded laboratory scientists.

ETHICAL CONSIDERATIONS

Guiding principles

This study is to be performed in accordance with the ethical principles of the Declaration of Helsinki (June 1964 and amended 1975, 1983, 1989, 1996, 2000, 2008 and Note of Clarification 2002 and 2004), ICH GCP Notes for Guidance on Good Clinical Practice (CPMP/ICH/135/95) annotated with Therapeutic Goods Administration comments, NHMRC National Statement on Ethical Conduct in Research Involving Humans (March 2007); the New Zealand Interim Good Clinical Research Practice Guidelines (Volume 2 1998 and Volume 3 2000) and ICH GCP Notes for Guidance on Good Clinical Practice (CPMP/ICH/135/95).

Ethical issues of the study

The two major ethical considerations in this study are:

- The enrolment of participants who are unable to provide their own informed consent

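### Prompts to look for barotrauma are written for the PHARLAP arm only, with no common ascertainment rule, so part of any excess in PHARLAP could reflect detection

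*Combined protocol and SAP*

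**What the plan says.** Under "Secondary outcome", barotrauma is one of three safety outcomes, with severe hypotension and serious adverse effects. The outcome entry has no definition. The only one in the protocol is an exclusion criterion: "Barotrauma (pneumothorax, pneumomediastinum, subcutaneous emphysema or any intercostal catheter for the treatment of air leak".

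For PHARLAP patients:

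- Under the heading on ongoing recruitment manoeuvres in the PHARLAP group, the desaturation paragraph reads "We recommend patients receive a chest x-ray for significant persistent desaturation to rule out barotrauma", and places this before any brief manoeuvre or further combined procedure.
- The contraindications to both the staircase and the brief manoeuvre include "Any radiographical evidence of pneumatoceles, subpleural cysts, or pericardial or mediastinal emphysema".
- During the staircase, a "new air leak through an intercostal catheter" is a reason to abandon it.
- These points recur. Combined procedures "should be performed daily for 5 days" unless an omission criterion is met, and brief manoeuvres are allowed up to a limit: "not more than a maximum of 4 manoeuvres per 24 hours".

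For control patients, the section on titrating FiO2 and PEEP says "If the patient has a significant desaturation, it is permissible to rapidly increase" the settings along the chart. The section on severe hypoxaemia then turns to rescue therapies. Neither mentions a chest film.

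For both arms, Appendix 3 marks a chest film and its download at baseline only. Barotrauma and adverse events are collected variables without restriction by arm, and Appendix 3 has adverse events recorded to ICU discharge.

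**The concern.** Several components of the barotrauma definition, pneumomediastinum for example, are found mainly by imaging. If one arm is prompted to image and the other is not, the observed rates can differ when the true rates do not. Bedside staff know the allocation. The documents state blinding only for the cytokine laboratory, and the independent radiologists classify the pattern of ARDS, not air leak.

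The likely direction is towards more recorded barotrauma in PHARLAP. That damages interpretation in two ways: a spurious excess could be read as harm, and a real excess could be dismissed as an artefact of imaging. The "Significance" section names barotrauma as one of the worries that shaped earlier trials of such strategies and presents this trial as the step before a phase III study. The safety comparison therefore needs to be readable.

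**Working it through.** **Text check.** Setting the two arms side by side:

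| Item | PHARLAP | Control |
|---|---|---|
| Response to desaturation | Brief manoeuvre; film recommended if significant and persistent | Move along FiO2/PEEP chart |
| Response to severe hypoxaemia | Brief manoeuvre if indicated, then rescue therapies | Rescue therapies |
| Radiographic contraindications in the ventilation strategy | Yes, for each manoeuvre | None |
| Scheduled chest film | Baseline | Baseline |
| Recording of barotrauma and adverse events | Yes | Yes |
| Common imaging window, adjudication or blinded reading for barotrauma | Not stated | Not stated |

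Recording is common to both arms. The prompts to look are not.

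**Arithmetic.** The plan gives no figure for barotrauma to reproduce; its sample size concerns ventilator free days. The inputs from the plan are 340 patients and the chi-square test for categorical variables. Equal allocation, 170 per arm, is assumed because the ratio is not stated. True and detected rates are also assumptions.

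Let p be the true rate in both arms, and dP and dC the proportions detected in PHARLAP and control. The observed rates are p × dP and p × dC, so the apparent risk ratio is dP / dC whatever the value of p.

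With p = 8%:

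- dC = 80%, dP = 90%: 0.08 × 0.80 = 6.4% and 0.08 × 0.90 = 7.2%; ratio 0.90 / 0.80 = 1.125, or 1.13 rounded. Expected events are 170 × 0.064 = 10.9 and 170 × 0.072 = 12.2.
- dC = 60%, dP = 90%: 0.08 × 0.60 = 4.8% and 7.2%; ratio 0.90 / 0.60 = 1.5. Expected events are 170 × 0.048 = 8.2 and 12.2.

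The exact chance of a significant two-sided chi-square test (uncorrected, 5% level, all pairs of binomial counts enumerated) is 5.8% in the first case and 14.8% in the second. With 90% detection in both arms it is 4.9%.

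**Sensitivity.** With full detection in PHARLAP and the same test:

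| Control detection | Apparent ratio | True rate 5% | True rate 10% | True rate 15% |
|---|---|---|---|---|
| 90% | 1.11 | 5.4% | 6.3% | 6.8% |
| 75% | 1.33 | 8.4% | 13.0% | 17.7% |
| 60% | 1.67 | 15.1% | 27.5% | 40.4% |
| 50% | 2.00 | 22.2% | 41.9% | 60.4% |

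A small detection gap barely moves the error rate; a large one matters. Nothing in the documents says which applies.

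**The case against.** The case against has weight on several points.

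- **Surveillance is conditional.** A reader might infer that PHARLAP patients have to be imaged before every manoeuvre. The text does not say so: the film is recommended, only for significant persistent desaturation, and the contraindication list requires no new film. The trigger is hypoxaemia, and the pilot reported better oxygenation with PHARLAP, so the number of extra films is unknown.
- **Control patients may be imaged anyway.** Appendix 3 lists study procedures. Its single film does not show that control patients go without clinical ones; usual-care imaging is neither required nor excluded.
- **The definition is not wholly radiographic.** The exclusion criterion includes an intercostal catheter placed for air leak, and subcutaneous emphysema, which can be found on examination. The gap is that the definition is not attached to the outcome.
- **Treated air leak is no complete cure.** A reader might take drained air leak as free of the problem. A pneumothorax usually has to be found before it is drained, and the decision to drain is made by staff not stated to be blinded.
- **The full analysis plan was still to come.** The protocol's statistical section defers detail to a later document, which could supply the missing rule.

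A reader might also extend the point to severe hypotension, since systolic pressure is a stopping criterion during the staircase while elsewhere "data will be collected on haemodynamics (daily central venous pressure, blood pressure and heart rate" is written for both arms. The documents do not support this. That daily list is collected because of possible confounding by co-interventions and is not named as the source of the hypotension outcome; vital signs and adverse events are listed separately. Baseline blood is drawn from an arterial line in both arms, so poorer pressure monitoring in control cannot be assumed. Hypotension during a staircase can also be a true effect of the manoeuvre.

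These points limit the size of the concern. They do not remove the difference in prompts or supply a common rule.

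**Conclusion.** The point holds as a risk of detection bias in the barotrauma comparison. The prompt to image and the radiographic contraindications are specific to PHARLAP, and no common or blinded ascertainment offsets them. Bias would most likely run against the intervention, and as planned it could not be separated from a real effect.

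Its size cannot be established. The apparent ratios of 1.13 and 1.5 rest on assumed detection of 80% or 60% in control against 90% in PHARLAP, with equal true rates; at an 8% true rate and 170 per arm the larger is a difference of about four detected events (12.2 − 8.2). A reader might infer that barotrauma is ranked above the other safety outcomes, or that bias has been shown. Neither follows: the three safety outcomes are unranked, and the documents show only that the comparison is open to bias. The change is cheap and worth making.

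**What to change.** Change measurement and reporting only, leaving patient care and imaging practice as they are.

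1. Attach the existing exclusion-criterion definition of barotrauma to the safety outcome, for events after randomisation, with the same observation window and source documents in both arms.
2. Pre-specify two reported comparisons: any barotrauma, and air leak treated with an intercostal catheter. Describe the second as less dependent on the number of films, though not independent of it and open to unblinded treatment decisions.
3. Record chest films on the case report form and report films per ventilated day by arm, so that a difference in any barotrauma is read against imaging intensity.

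The cost is outcome and analysis-plan wording plus one case report form item. The downside is that treated events will be few, so that comparison will be imprecise.
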